CTSU sites should follow procedures outlined in the protocol for Site registration, Patient Enrollment, Adverse Event Reporting, Data Submission (including ancillary studies), and Drug Procurement.

For patient eligibility or treatment-related questions Contact the Study PI of the Coordinating Group.

[figure not shown]
For questions unrelated to patient eligibility, treatment, or data submission contact the CTSU Help Desk by phone or e-mail:

CTSU General Information Line – [name], or [contact]. All calls and correspondence will be triaged to the appropriate CTSU representative.

For detailed information on the regulatory and monitoring procedures for CTSU sites please review the CTSU Regulatory and Monitoring Procedures policy located on the CTSU members' website https://www.ctsu.org

The CTSU Web site is located at https://www.ctsu.org

Schema

Accrual = 1,000 patients

- Anastrozole will be given 1mg, po daily for 12 months.

 AIMSS diagnosis will be determined clinically by oncology MD or Nurse when patient complains of joint symptoms. See Section 5.

 Decision whether to continue anastrozole or to start a treatment for AIMSS will be made by patient & MD discussion. See Section 5.

 Blood collection is mandatory for pharmacogenomics as outlined in Section 10. If unable to collect at baseline, please collect at any other time point.

Cancer Research Group Version Date: April 13, 2023

1. Introduction

1.1 Rationale for Proposed Study

1.1.1 Significance of the Condition

Breast cancer is one of the most prevalent cancers with 207,090 new cases of breast cancer and 39,840 deaths in women predicted for 2010 in the United States⁽¹⁾. Aromatase inhibitors (AIs) are used as first-line adjuvant therapy for postmenopausal women with early stage breast cancer⁽²⁾. The effectiveness of current therapy is widely recognized to be compromised by poor compliance because of aromatase inhibitor-associated musculoskeletal symptoms (AIMSS), a syndrome that affects up to 40-50% of women who take these medications. The syndrome that was not recognized during the registration trials for this class of drugs⁽³⁾, it can lead to discontinuation in up to 24% of women over 2 years ^(4,5). Knowledge that can be used to prevent discontinuation of these important agents because of severe AIMSS is urgently needed.

The NCI Division of Cancer Prevention has recognized AIMSS as a priority area for future study. The symptoms are associated with a high rate of AI discontinuation and therefore compromise survival outcomes at great cost to both patients and society. Very little is known about AIMSS, or how to predict who is at risk for the condition, or for discontinuing therapy because of the symptoms. This study will provide a basis for comprehensive assessment of risk factors at the patient-reported outcomes, phenotypic, and laboratory levels. We will explore the natural history of AIMSS in different ethnic populations, and will validate previously reported genetic determinants of the development of AIMSS.

A common problem with multicenter GWAS studies of very large sample size, especially in the absence of measurable diagnostic parameters, is inclusion of heterogeneous groups of patients⁽⁶⁾. In addition to assessing pharmacogenomic predictors, this study involves specification of a pre-defined AIMSS phenotype and collection of patient-reported outcomes (PROs). As such, these data will have clinical utility by clarifying the factors associated with aromatase inhibitor discontinuation and thus guiding clinicians towards interventions to improve adherence. Coupled with other studies, the long-term goals are to develop a gene signature that will be used to better guide the selection of endocrine interventions for patients with breast cancer.

Etiology and Pathophysiology

The underlying physiology of AIMSS remains obscure. A small exploratory case control study did not find a role for commonly encountered cytokines in AIMSS ⁽⁷⁾. The role of estrogen and estrogen metabolites remains a possible explanatory variable, as well as new cytokines such as IL-17. This newly described cytokine has been implicated in disorders such as rheumatoid arthritis and other

autoimmune diseases ⁽⁸⁾, and has been specifically linked to articular nociception in animal models of arthritis⁽⁹⁾.

AIMSS Phenotype: The large studies to date of Als (ATAC, BIG I-98, E1Z03) have been limited by the absence of a clearly defined phenotype for AIMSS ⁽¹⁰⁾. Retrospective analyses have provided some information that clearly cannot replace (PROs). The lack of good prospective PROs represents a major gap as a well-defined phenotype is necessary in order to identify useful genomic associations. Methods evaluating possible predictors such as the use of MRI of the wrists for tenosynovitis are expensive and have not been definitive ⁽¹¹⁾ and patient-reported symptoms are used and may represent the most useful clinical phenotype.

The exemestane and letrozole pharmacogenomics (ELPh) study, conducted by the Consortium on Breast Pharmacogenomics (COBRA), has provided important data not only regarding the prevalence of the symptoms and drug discontinuation but also for PRO by using the Health Assessment Questionnaire (HAQ), a commonly used rheumatology instrument. [name] and [name] of ECOG are co-founders of the COBRA group. In this prospective comparison of exemestane and letrozole, patients were randomly assigned to either letrozole or exemestane and were evaluated at predefined intervals by study team members and referred to a rheumatologist based upon change in HAQ scores and pain ratings on a visual analog scale (VAS). The study showed that the predefined symptomatic criteria based on the HAQ and VAS successfully provided a means of case definition of an otherwise difficult-to-characterize syndrome (4,5). Improvement or worsening of HAQ score was defined as a decrease or increase, respectively, of more than 0.22 based on data provided from the rheumatology literature⁽¹²⁾. However, the sensitivity, specificity, and generalizability of the ELPh clinical criteria for defining AIMSS clearly need to be confirmed in a larger cohort of a diverse patient population and in other clinical settings. Data from the ELPh study for the first 100 patients showed that median time to onset of symptoms was 1.6 months (range 0.4-10 months), and median time to study discontinuation (for those who stopped taking AI) was 6.1 months (range 2.2-13 months) (4).

Anastrozole was not studied in the ELPh trial, representing a gap in knowledge both as it is a widely prescribed AI, and because anastrozole associated musculoskeletal symptoms have not been phenotypically characterized with the HAQ. Furthermore, as the patients studied by the ELPh and NCIC Clinical Trials Group MA.27 (described below) populations are predominantly Caucasian, further studies in minority populations are urgently needed.

Genetic Predictors of AIMSS: Pharmacogenomic predictors may help identify women at risk for AIMSS since genetic variants that are associated with AI pharmacokinetics, with the effects of estrogen deprivation on bone and other phenotypes have already been described. We briefly review recent important findings that emphasize the importance of this concept as well as its feasibility.

Previous studies by the PI with COBRA investigators identified genetic predictors, such as polymorphisms in estrogen receptors (ESR), or genes encoding for cytochrome P450 enzymes (CYP), of tamoxifen effects. Estrogen receptor subtypes may influence lipid metabolism (13) and bone density (14). Furthermore, CYP polymorphisms are important in predicting discontinuation of tamoxifen (15), and hot flashes (16). Our preliminary data suggest that variants in ESR predict development of AIMSS (Manuscript in preparation). These findings provide an important model for exploration of genetic predictors of side effects of Als. Additional recent work has identified potential genetic determinants of the pharmacokinetics and pharmacodynamics of the Als that may also explain variability in responses to Als. (17-21).

The first evidence for the existence of genetic predictors of AIMSS came from an analysis of 293 cases and 585 controls from the MA.27 trial, a large study which compared exemestane and anastrozole. Genome wide associations (GWAS) and functional genomic studies identified novel single nucleotide polymorphisms (SNPs) and a gene related to IL-17 as associated with AIMSS⁽¹⁷⁾. These findings were recognized as important and should be confirmed in large prospective studies ⁽²²⁾. However, few studies conducted or planned to date have included a predefined phenotype, PROs or specimens evaluable for pharmacogenomics.

Review of available data from the MA27 and the ELPh studies has identified ten SNPs that may be relevant to AIMSS syndrome. In the MA27 dataset, the most striking P values (1E-06) were for three SNPs on chromosome 14, rs7158782, rs7159713, rs2369049, which were all close to the T Cell leukemia 1A (TCL1A) gene, a fourth SNP, rs11849538, was imputed. The ELPh study also identified the latter two SNPs, and four other SNPs. These were rs2296972, the serotonin receptor subtype 2A, rs2347868 and rs9340835 associated with estrogen receptor 1, and rs4646 associated with CYP19A1. An additional two SNPs have been identified in studies of severe large joint arthritis. These are rs2234693 in the ESR1 gene, and rs1062033 in the CYP19A1 gene (22a).

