2.1 Primary Objectives

To validate previously identified associations between 10 specific single nucleotide polymorphisms (SNPs) and discontinuation of treatment with Als due to the development of musculoskeletal symptoms (MSS) among women with breast cancer.

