9.1 Statistical considerations for primary objective of SNP validation

Patients will be classified into two groups based on whether or not they discontinued treatment due to MSS. Hardy-Weinberg equilibrium will be evaluated within each racial subset. SNP genotypes will be coded as additive effects on the log odds ratio by coding as 0, 1 or 2 for the count of the minor allele. Logistic regression will be used to test the association between having a minor allele and the log odds of discontinuation of treatment, adjusting for covariates. We plan to enroll 1000 patients and follow them for development of symptoms. Minor allele frequencies reported by Ingle et al. were assumed for the 4 SNPs associated with the TCL1A gene, and preliminary results from the ELPH study were used to estimate minor allele frequencies associated with the ESR gene. A Bonferroni adjustment will be used to account for the simultaneous testing of 10 SNPs; a one-sided p-value of 0.0025 will be considered statistically significant. For purposes of illustrating statistical power, we assume that Hardy-

Weinberg equilibrium exists in the allele distribution and that the minor allele is associated with *higher* proportions of discontinuation of treatment due to development of symptoms. Table 1 shows the genes, SNPs, and representative minor allele frequencies observed in previous studies. Table 2 shows odds ratios for the effect of each minor allele that will be detectable with 80% power for overall discontinuation rates of 20% or 30% and a range of plausible minor allele frequencies, given a sample size of 1000 patients and using a one-sided Cochran-Armitage trend test. The table also shows detectable odds ratios for the subsets of Caucasian (n=600) and African-American and Asian patients (n=200 patients each).

Table 1. SNPs to be validated

SNP	Gene	Rank (Ingle)	Rank (ELPH)	Minor Allele Frequency (MAF)
rs7158782	TCL1A	1		0.189 among cases, 0.109 among controls (0.2 ELPH)
rs7159713	TCL1A	2		0.189 (0.19 ELPH)
rs2369049	TCL1A	3	4	0.176 (.18 ELPH)
rs11849538	TCL1A	4	9	0.15 (ELPH)
rs2296972	HTR2A		1	0.37 (ELPH)
rs2347868	ESR1		2	0.23
rs9340835	ESR1		3	0.35
rs2234693	ESR1			0.45 (Riancho)
rs1062033	CYP19A1			0.44 (Riancho)
rs4646	CYP19A1		5	0.28

Table 2. Odds Ratios for Effect of Each Minor Allele Detectable with 80% Power (Additive Model)

Proportion Discontinuing	MAF	N=1000	N=600	N=200
20%	10%	1.88	2.23	3.89
30%	10%	1.78	2.10	3.65
20%	20%	1.63	1.87	2.94
30%	20%	1.55	1.76	2.70

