20%	30%	1.55	1.76	2.66
30%	30%	1.47	1.65	2.42
20%	40%	1.52	1.72	2.59
30%	40%	1.44	1.61	2.33

9.2 Secondary Endpoint Analyses

The association of other SNPs in the ESR, TCL1A, and CYP19A1 genes with discontinuation of treatment due to MSS will be explored using a candidate gene approach. In this exploratory analysis, the prevalence of treatment

discontinuation will be compared between patients who do and do not have the variant genotype, modeling the effects as additive, dominant, and recessive. Correlations among SNPs will be estimated, and linkage disequilibrium among pairs of SNPs will be characterized. Logistic regression models, with treatment discontinuation as the outcome variable, will be used to explore the association with SNPs, adjusting for important clinical factors. No adjustment for multiple comparisons is planned, but only the top ranking SNPs that were not part of the primary validation study will be further explored.

Other endpoints, including the proportions of patients with treatment discontinuation for any reason, the proportion of patients with symptoms determined not to be from other known etiologies, and the proportion of patients whose symptoms improve when the AI is discontinued, will be similarly explored. Time to discontinuation of treatment and time to development of symptoms will be explored using proportional hazards models adjusting for significant genotypic and clinical predictors. Kaplan-Meier plots will be used to graphically portray the associations. Hispanics are the fastest growing demographic group in the US population, and there are 17,100 new breast cancer cases and 2400 breast cancer deaths expected in this demographic group in 2012³⁷. The Hispanic demographic group may have unique attitudes, beliefs and behaviors related to medication adherence with AI.³⁸⁻⁴⁰ Exploratory analyses to determine whether effects are different in patients with Hispanic ethnicity will also be performed.

Previous studies have suggested that patients who experience specific adverse events associated with endocrine therapy may have improved recurrence-free (RFS) and overall survival (OS) compared to those who do not develop these symptoms (42,43). RFS ad OS will be described for the entire study population and for racial and ethnic subsets. Differences in RFS and OS between patients who do or do not develop AIMSS will be explored.

9.3 Statistical Considerations For Patient-Reported Outcomes

Rev. 11/13

Rev. 11/13

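### Nine of the ten primary SNPs share three genes, four of them TCL1A, yet section 9.1 tests and corrects them as ten separate associations, with no joint model and no use of their correlation

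*Combined protocol and SAP*

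**What the plan says.** The primary objective (section 2.1) is "To validate previously identified associations between 10 specific single nucleotide polymorphisms (SNPs) and discontinuation of treatment with Als" because of musculoskeletal symptoms. Section 9.1 codes each SNP as 0, 1 or 2 minor alleles and tests it by covariate-adjusted logistic regression. On multiplicity it says "A Bonferroni adjustment will be used to account for the simultaneous testing of 10 SNPs", and then "a one-sided p-value of 0.0025 will be considered statistically significant".

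Table 1 groups the ten SNPs by gene:

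- TCL1A: four SNPs
- ESR1: three SNPs
- CYP19A1: two SNPs
- HTR2A: one SNP

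Section 1.1.1 gives the origin of the TCL1A group. Three were found together in MA.27, described as "three SNPs on chromosome 14, rs7158782, rs7159713, rs2369049, which were all close to the T Cell leukemia 1A (TCL1A) gene", and "a fourth SNP, rs11849538, was imputed". Of the second study it says "The ELPh study also identified the latter two SNPs, and four other SNPs".

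LD appears once, in section 9.2: "Correlations among SNPs will be estimated, and linkage disequilibrium among pairs of SNPs will be characterized". That paragraph concerns other SNPs in the same genes, calls itself exploratory, and limits further work to SNPs outside the primary validation set.

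**The concern.** SNPs close together at one gene may be correlated. If so, single-SNP tests of neighbours partly repeat the same test, and one true signal can make several of them significant. One-at-a-time models cannot show whether a second SNP in a gene adds anything to the first. Section 9.1 names no lead SNP, no joint or conditional model, and no rule for several hits in one gene.

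This matters for later use. Section 10.1 hopes to identify a marker of risk, and objective 2.2.3 aims at a gene signature. Both are helped by knowing whether four TCL1A hits are one signal or more. The source populations were mainly Caucasian (section 1.1.1), while the plan enrols about 200 Asian and 200 African-American patients. LD may differ between these groups, but 9.1 checks only Hardy-Weinberg equilibrium by race.

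A smaller matter is that a divisor of ten is stricter than a correlated family needs.

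**Working it through.** **The plan's own figures.** 0.025/10 = 0.0025, as stated. Table 2 reproduces with a one-sided Cochran-Armitage test under Hardy-Weinberg equilibrium. At the printed odds ratios all 24 cells give 80.5% to 81.9% power. For example, with N = 1000 and MAF 20%, an odds ratio of 1.63 at 20% discontinuation gives 80.9%.

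**Range of r².** The documents give none, so it is an assumption. Allele frequencies bound it. For MAFs p > q, the largest r² is q(1−p)/[p(1−q)].

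- TCL1A, ELPh frequencies 0.20, 0.19, 0.18 and 0.15: the six caps are 0.94, 0.94, 0.88, 0.80, 0.75 and 0.71. The smallest is 0.15×0.80/(0.20×0.85) = 0.706. A common r² for all six pairs therefore cannot exceed about 0.7.
- ESR1, 0.23 with 0.45: 0.23×0.55/(0.45×0.77) = 0.37.
- CYP19A1, 0.28 with 0.44: 0.28×0.56/(0.44×0.72) = 0.495.

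**How many TCL1A SNPs one signal would bring.** Take one causal SNP at 80% power. The critical value is 2.807, so its mean statistic is 2.807 + 0.842 = 3.649. A proxy has mean √r² × 3.649. At r² = 0.5 that is 2.580, so the proxy's own power is Φ(2.580 − 2.807) = 41%. Simulating four equally correlated normal statistics, minor alleles positively coupled, gives:

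| Common r² | Mean number declared, given a hit | Two or more, given a hit | Three or more, given a hit |
|---|---|---|---|
| 0.25 | 1.6 | 39% | 15% |
| 0.34 | 1.9 | 52% | 27% |
| 0.50 | 2.5 | 70% | 48% |
| 0.70 | 3.1 | 85% | 71% |

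A haplotype simulation used the ELPh frequencies, N = 1000, odds ratio 1.63 and 20% discontinuation. It gives three or more, given a hit, in 87% of trials at D′ = 1, 73% at 0.9, 41% at 0.7 and 13% at 0.5.

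**Error rate and significance level.** The level in the third column is the one at which the maximum of the ten statistics exceeds its critical value in 2.5% of null trials. Power is for a SNP with 80% power at 0.0025, that is Φ(3.649 − critical value).

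| LD assumed | Family-wise error at 0.0025 | Level for 0.025 overall | Power |
|---|---|---|---|
| None | 0.0248 | 0.0025 | 80.1% |
| TCL1A pairs at their caps | 0.020 | about 0.0031 | 82% |
| All three genes at their caps | 0.018 | about 0.0035 | 83% |

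**The case against.** The strongest reply is that nothing in 9.1 is invalid. Bonferroni controls the family-wise error whatever the correlation. The objective is to validate associations of named SNPs, and a proxy that is truly associated is a correct replication, not a false positive. A risk marker need be neither causal nor independent of its neighbours. Table 1 prints the gene beside each SNP, and no passage defines success as a count out of ten. All of this stands, and it makes the point an improvement to the plan, not an error in it.

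Two stronger readings are tempting, and the documents support neither.

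- A reader might infer that a single TCL1A signal would usually appear as three or four validated SNPs. The similar MA.27 p-values, the near-equal frequencies and the imputed fourth SNP are compatible with strong LD, but no r² or D′ is given. ELPh is said to have identified only two of the four, and Table 1 ranks only those two for ELPh. At the planned power, given a hit, three or more becomes the majority result only above r² of about 0.52.
- A reader might infer that testing neighbours separately inflates false positives. It does the reverse: under LD the actual error falls below 0.025.

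Section 9.2 does plan to describe LD, which goes part of the way. What it lacks is any consequence for the primary conclusion.

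Conditional models also have low power under strong LD. A rule that withheld validation from a SNP unless it survived such a model would discard real replications, so the single-SNP tests should remain the validation step.

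**Conclusion.** The gap is real but modest. Section 9.1 makes no use of the gene grouping that Table 1 shows, and it cannot say whether several hits in one gene are one signal or more.

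How often this would matter depends on an r² that the documents do not give. On the one-causal-SNP model, multiple TCL1A hits pass half of the trials with a hit from r² of about 0.34. Low r² would make the issue small.

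The 0.0025 level is valid and somewhat conservative under LD. The unused power is at most about 3 percentage points with every pair at its frequency cap, and almost none without LD. These figures rest on positive coupling of the minor alleles, on Table 1 frequencies holding in this cohort, and on pooled LD across racial groups.

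The changes are worth making because they cost little and lose no power.

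**What to change.** Two changes to section 9.1, made before the genotype results are analysed:

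1. Replace 0.025/10 with a level from the permutation distribution of the maximum of the ten one-sided statistics. Permute whole ten-SNP genotype vectors within race. This keeps the correlation among SNPs and the link between outcome and covariates. The level should fall at about 0.0025 to 0.0035, with power of about 80% to 83%. Apart from simulation error, it is never worse than Bonferroni.
2. Keep the single-SNP tests as the validation of each listed SNP. When more than one SNP in a gene is significant, fit one model for that gene with all its listed SNPs and the same covariates, and judge each at a conditional threshold stated in advance. Report LD by racial group. State the number of loci beside the number of SNPs, and use a phrase such as *locus validated, SNP not resolved* where the joint model cannot separate them.

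The cost is SAP wording and a few extra fits, with no new patients or assays. The downside is that fewer independent signals may be claimed, because conditional models are weak when SNPs are strongly correlated.

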1.1.2 Studying the Decision to Discontinue Aromatase Inhibitors

Compliance is an important issue, as many patients do not fill their prescriptions for Als ⁽²³⁾. The basis for the patient's decision to discontinue Al therapy has not been studied. On the basis of anecdotal observations of our community oncologists, patients are torn between their fear of recurrence and the perceived burden of treatment. Als are one of the few agents that have pain as a side effect. Patient answers to questions about their fear of recurrence, perceived treatment burden, burden due to co-morbidities, and adherence behaviors may provide further insights to patient decision-making and compliance.

The significant role of patient reported outcomes as a possible determinant in the decision to discontinue Als was a central finding in ECOG 1Z03 and presented by [name] at the 2011 San

Antonio Breast Conference ⁽²⁴⁾. Further study of patient reported outcomes may lead to robust bedside assessments of the risk of discontinuation.

1.1.3 Studying the use of paper forms or the PROMIS electronic format for data entry

Collection of patient rated outcomes is a critical component of these kinds of studies, and incomplete data collection during follow-up represents a major challenge both logistically and to the validity of these studies. The NIH has developed a Web-based system for recording patient reported outcomes during clinical trials, the Patient Reported Outcomes Management Information System (PROMIS) that will enable the efficient collection of patient reported outcomes and decrease the logistical burdens on office practices for patients on clinical trials. The PROMIS Assessment Center is the web-based platform for dissemination of NIH PROMIS measures. The assessment center can be used to administer patient rated outcome instruments, monitor accrual, manage data, send reminders to patients, be used to deliver custom researcher developed content, and has numerous features that support both simple and complicated accrual designs (branching, multiple arms, multiple time points, etc.). (25) [name], an ECOG member, has been a key participant in the development of the PROMIS system and is Director of the PROMIS Statistical Center. Studies undertaken by the PROMIS staff have shown there is excellent satisfaction with the PROMIS Assessment Center (26) for patients with visual and other impairments. There is no charge for using the PROMIS system. Data is kept secure behind firewalls. Data that is entered will be the property of ECOG and can be downloaded directly to the ECOG system. With the current popularity of smart phones in the breast cancer patient population, we think the time is ripe to test its' use in a cooperative group trial setting.

The symptom instruments used will build upon the work in the NIH Patient Reported Outcomes project to develop better symptom instruments, through use of the PROMIS Physical Function 20 Form and the PROMIS Assessment Center. This will support the development of better symptom and quality of life measurements and begin to integrate the PROMIS project within the Cancer Cooperative Groups. Experience in using the instruments and the PROMIS Assessment Center will lead to new ways for cooperative groups to collect patient rated outcome data and reduce attrition.

Secondary objective 2.2.6 is to assess the **feasibility** of the on-line **PROMIS** platform for collecting patient-reported outcomes in the setting of a cooperative group clinical trial. We plan to make all of the patient-reported quality of life instruments available through the PROMIS web site.

2. Objectives

